## **STUDY MONITORING AND DOCUMENTATION**

The Principal Investigator will monitor the study and assess the need for amendments as the study progresses. A protocol revision may be necessary for reasons including but not limited to rights, safety of participants, welfare of participants, and thus, an amendment will be required. Appropriate approvals (i.e., IRB) of the revised protocol must be obtained prior to implementation at each site.

### **Site Documentation**

All study documents included in this protocol that will be presented to subjects will be submitted to the IRB for approval. The primary site will maintain a study binder for all sites that will include the following:

- Enrollment log of patients that have consented to be in the study (electronic version)
- Protocol deviation log (electronic version)
- Adverse event log (electronic version)
- Investigator protocol and amendments
- IRB submissions, modifications, and renewals
- Data safety monitoring committee reports
- IRB approved consent form
- Data collection forms

## Monitoring

Monitoring will be conducted by the data safety monitoring board (DSMB) throughout the study to ensure that the study is conducted in accordance with the study protocol. By verifying compliance, monitoring helps to safeguard the subject safety, ensure data quality, and provide ongoing training and support to ensure compliance.

Data verification will occur at 6-month intervals to verify data, assess continued compliance with protocol.

An interim analysis will be completed at 6 months from the study commencement date. The purpose of the interim analysis is to discern whether the trial can be stopped for early benefit, as well as evaluate for safety and efficacy. Interim data analyses will be presented to the Data Safety and Monitoring Board for their review and recommendation.

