## **STATISTICAL CONSIDERATIONS**

Calculations of sample size were based on comparisons of UTI rates in the nitrofurantoin and placebo arms. According to published results, the UTI rate in the placebo arm was 32% and approximately a 14-15% reduction was observed in the treatment arm. Using this information, we designed our study to mimic these findings, and assumed a UTI reduction rate of 18% in the nitrofurantoin arm could be observed in our clinical setting. Based on this assumption, total sample size of 164 patients was projected to achieve 80% power with a two-sided  $\alpha$  error of 0.05. We increased the total sample size to 180 to allow for a 10% dropout rate. However, due to primary investigator timeline and lack of attrition, recruitment ceased once the sample size of 164 was reached. The power was calculated by using the PASS 15 (2017, NCSS, LLC. Kaysville, Utah, USA). All analyses were conducted using an intent-to-treat principle, which included all women

randomized and not withdrawn from the study. A per-protocol analysis was also performed, and only included patients that completed the study.

Categorical data were compared using X or Fisher's Exact test where appropriate. Continuous variables were compared using Student's t-test or Wilcoxon rank sum where appropriate, and are presented as mean±standard deviation or median (interquartile range). We estimated risks for UTI with odds ratio (OR) and corresponding 95% confidence intervals (95% CI) calculated using logistic regression. A P value <0.05 defined statistical significance. All analyses were conducted using SAS Enterprise Guide version 7.1 (SAS Institute, Cary, NC). No interim analysis was performed.

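### Does the 6-month look for early benefit, planned without a stopping boundary and later reported as not done, undermine the 5% error level?

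*Combined protocol and SAP*

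**What the plan says.** Under Monitoring, in the future tense: "An interim analysis will be completed at 6 months from the study commencement date". Its purpose is given as "The purpose of the interim analysis is to discern whether the trial can be stopped for early benefit", with safety and efficacy also to be evaluated. On who decides: "Interim data analyses will be presented to the Data Safety and Monitoring Board for their review and recommendation". No boundary, alpha allocation or information fraction appears there or elsewhere. The DSMB section describes that board's work as the review of adverse events, with a report every six months.

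Statistical Considerations is in the past tense. On sizing, a "total sample size of 164 patients was projected to achieve 80% power" at a two-sided 0.05 level; the target was raised to 180 for dropout, but "recruitment ceased once the sample size of 164 was reached", with the investigator's timeline and the lack of attrition given as reasons. On testing: "A P value <0.05 defined statistical significance". On the planned look: "No interim analysis was performed".

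Neither section refers to the other.

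**The concern.** An efficacy look with power to stop the trial, but no decision rule, is a recognised route to a false positive. If the data are tested once midway and again at the end, each time at 0.05, the chance of at least one false rejection exceeds 5%. A statement elsewhere in the same document that no look took place, with no word on when or why it was abandoned, invites doubt about which section to believe. Recruitment also closed at 164 rather than 180, so a reader might ask whether anyone had seen results by arm before that decision. At stake would be the type I error of the primary comparison of UTI rates and the credibility of the stopping point.

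**Working it through.** **1. Is 164 a fixed-design size?** Inputs from Statistical Considerations: placebo rate 32%, reduction 18%, two-sided 0.05, 80% power. Two readings are assumed: the reduction is 18 percentage points (32% v 14%), and allocation is 1:1. With unpooled variance,

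n per arm = (1.960 + 0.842)² × (0.32×0.68 + 0.14×0.86) / 0.18² = 7.849 × 0.338 / 0.0324 = 81.9, so 82 per arm and 164 in total.

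The stated figure reproduces exactly. Power at 82 per arm is Φ(0.18/√(0.338/82) − 1.960) = Φ(0.844) = 80.1%. The pooled formula gives 170 in total, and 78.7% power at 164. Reading 18% as the treated-arm rate gives 294 to 298, and reading it as a relative reduction gives 1,946 to 1,952, so neither fits. The trial was therefore sized for one test, with no allowance for a look.

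**2. Is closing at 164 early stopping?** The target of 180 is the calculated 164 plus a dropout allowance (164 × 1.1 = 180.4). Closing at 164 completes the calculated size and forgoes only the allowance, for a stated reason.

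**3. Type I error as reported.** With no interim test, the error is that of the final test alone. The exact size was found by enumerating binomial counts at 82 per arm, using the uncorrected chi-square unless an expected count is below 5, and then Fisher's test. The plan says only "Fisher's Exact test where appropriate", so that switch is an assumption. At common UTI rates of 15%, 23% and 32% the size is 0.0487, 0.0505 and 0.0502.

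**4. Hypothetical: one unadjusted look.** Assume P<0.05 at both looks. The documents give no accrual rate, so the number available at 6 months is unknown and is varied here.

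Overall error = P(reject at the look) + P(continue, then reject at the end).

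The benefit-only column counts interim rejections in favour of nitrofurantoin only; the final test stays two-sided. That column matches the stated purpose of the look.

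| Per arm at the look | Benefit only (UTI rate 15 / 23 / 32%) | Either direction (15 / 23 / 32%) |
|---|---|---|
| 12 | 0.0517 / 0.0567 / 0.0607 | 0.0547 / 0.0629 / 0.0711 |
| 20 | 0.0576 / 0.0662 / 0.0714 | 0.0665 / 0.0820 / 0.0927 |
| 41 | 0.0644 / 0.0675 / 0.0666 | 0.0800 / 0.0846 / 0.0830 |
| 62 | 0.0594 / 0.0614 / 0.0616 | 0.0702 / 0.0723 / 0.0730 |

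A normal approximation agrees. At half the information the two statistics correlate at √0.5 = 0.707, and the either-direction error is 1 − P(|Z₁|<1.96, |Z₂|<1.96) = 0.0831. The excess over 0.05 is 0.0331; half of it belongs to the benefit side, giving 0.05 + 0.0331/2 = 0.0666.

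**5. Which section describes what happened?** Monitoring states an intention. Statistical Considerations reports the close of recruitment and the absence of an interim. The second is the later account and is explicit on the fact in question, so step 3 applies and step 4 does not.

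**The case for a change.** The strongest reply is that the protocol sets itself a higher standard. Study Monitoring and Documentation requires approval of a revised protocol before it is put into effect, and Protocol Deviations requires every deviation to be logged. Statistical Considerations explains the shortfall from 180 but not the missing look. The Randomization section masks participants and investigators but exempts the statistician and the pharmacist, so masking alone does not show that no one had seen outcomes by arm. A benefit look with no rule was also poorly specified from the start.

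Most of this is accurate: the look was under-specified and its omission goes unexplained. But amendments, the deviation log and DSMB reports are kept in the study binder listed under Site Documentation, so silence here does not show that no record exists. The statistician's access to allocation is not evidence that outcomes were compared, and nothing in the documents suggests that a look took place. A rule for a look that was never made governs nothing.

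The larger error rates, up to 9.3%, also assume stopping at P<0.05 in either direction, whereas the stated reason for stopping is benefit. As written, the look has no threshold, so its error rate is undefined rather than inflated.

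**Conclusion.** The concern does not call for a change. The two sections are a plan and a later report that one step of it was not carried out. On that report a single 0.05 level is correct and needs no adjustment. The benefit-only range of 5.2% to 7.1% belongs to a look that the documents say was not made, at a threshold they do not assign.

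What remains is a gap in explanation: when, why and by what route the look was dropped. Filling it would help a reader but would change no estimate, test or conclusion.

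This rests on the report under Statistical Considerations being accurate. For the sample-size check it also rests on 1:1 allocation and an 18-point reduction. If a look by arm had in fact occurred, the question of adjustment would reopen.

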## Study Drug Information

- **Drug:** Nitrofurantoin 100 mg capsules, with matched placebo, will be provided by Central Compounding Center South
- **Storage:** all study medications will be in a secure, locked, climate controlled location accessible only to authorized study personnel. All study medications will be maintained at controlled room temperature between 20-25°C with excursions permitted from 15-30°C.
- The principal investigator and/or her designee(s) will be responsible for ensuring accountability of study medications is maintained throughout the study for all study medications that is received, dispensed, and disposed of per institutional standards of procedures. This log will be maintained on the electronic application, Vestigo.
- Only participants enrolled and randomized in this study may receive study medications
- All unused study medications will be destroyed per the institution's destruction policy

## Protocol Deviations

Protocol deviations will be documented and logged on the Protocol Deviations log (electronic version). This will be done for every protocol related deviation related to any portion of the study timeline. Deviations will be reviewed and evaluated on an ongoing basis, and, as necessary, appropriate corrective and preventive actions (including notification, re-training, or discontinuation) will be put in place.

## Data Safety Monitoring Board (DSMB)

A data safety monitoring board (DSMB) will be comprised of an external physician and research nurse. They will be tasked to review all adverse events that occur across both study sites. A semi-annual report of all adverse events will be generated and sent to the Data Safety Monitoring Committee every 6 months.

All Serious Adverse Events (SAEs) will be reported to the DSMB via email within 2 days of site staff being informed of its occurrence. The PI and research nurse will be cc'd on all communications with the DSMB. Copies of de-identified source documentation regarding the SAE will be included, as well as other clinically meaningful documentation.

The PI will be responsible for ensuring that all sites comply with the DSMB requests.

## Reporting Adverse Events

Adverse events (AE) will be recorded and reported per the criteria and timeline below.

All AEs must be recorded and entered into the AE log and REDCap. An event number will be assigned by each site and recorded.

SAEs must be reported to the DSMB within two business days as outlined above in the Data Safety Monitoring Committee section.

Reportable AEs include those determined to be related to the study medication. AEs not related to the study medications will not be collected. Please note that underlying diseases are not reportable AEs unless there is an increase in severity or frequency during the course of the investigation. Death should not be recorded as an AE, but as an outcome of a specific SAE.

Any participant that suffers an allergic reaction to the study medications will be unblinded. This will be a reported adverse event that will also be reported to the DSMB, as outlined above.

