### Secondary Objectives

1. To evaluate adverse outcomes related to study medications in each group
2. To evaluate medication compliance

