### **Secondary Outcome Measures**

1. Adverse Events
  - a. Any adverse event related to drug administration will be reported. Adverse events not related to medication administration will not be collected. Please refer to section on Adverse Events for details of reportable criteria.
2. Medication compliance
  - a. All participants will need to complete a medication diary during the study drug treatment period. They will be asked to return this diary at their follow up. Medication compliance will be assessed and analyzed by way of these medication diaries.

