## Adverse Event Definitions

Adverse Event: any untoward medical occurrence, unintended disease or injury, or any untoward clinical signs (including abnormal laboratory finding) in subjects, whether or not related to study medications

Serious Adverse Event: an adverse event that led to:

- Death
- Serious deterioration in the health of the subject that either resulted in
  - A life-threatening illness or injury

- A permanent impairment of a body structure or a body function
- Medical or surgical intervention to prevent life-threatening illness or injury or permanent impairment to a body structure or body function

Unrelated: No evidence that the timing of the AE has a relationship to the time study medications were taken

Possibly Related: The AE has a timely relationship to the study medications, however a potential alternative etiology may be responsible for the AE

Probably Related: The AE has a timely relationship to the study medications and the causative relationship can clearly be established. No potential alternative etiology is apparent.

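### The safety sections conflict on whether adverse events judged unrelated, above all serious ones, are collected and sent to the DSMB, and on the SAE reporting clock

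*Combined protocol and SAP*

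**What the plan says.** All sections cited are in the combined protocol and SAP.

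- **Secondary Objectives**, first item: "To evaluate adverse outcomes related to study medications in each group".
- **Secondary Outcome Measures**: drug-related events are to be reported, and "Adverse events not related to medication administration will not be collected".
- **Reporting Adverse Events**: "All AEs must be recorded and entered into the AE log and REDCap". Further down: "Reportable AEs include those determined to be related to the study medication", followed by "AEs not related to the study medications will not be collected". On serious events: "SAEs must be reported to the DSMB within two business days".
- **Data Safety Monitoring Board (DSMB)**: the board reviews all adverse events at both sites and is sent a report of all adverse events every six months. In addition, "All Serious Adverse Events (SAEs) will be reported to the DSMB via email within 2 days" of site staff learning of them, with de-identified source documents.
- **Adverse Event Definitions**: an AE is an untoward occurrence "in subjects, whether or not related to study medications". An SAE is an AE meeting a seriousness criterion. Relatedness has three levels: unrelated, possibly related and probably related.

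**The concern.** The collection rule and the oversight rule cannot both be followed for an event judged unrelated. The case that matters most is a serious one. The protocol treats death as an outcome of an SAE, so a death judged unrelated falls into the same gap.

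Two things are at stake. The first is oversight: if sites applied the exclusion literally, the DSMB would not receive every serious event that its own section promises it. The second is what can be done with the data. An event that was never collected cannot be audited, reclassified if the causality call is later questioned, or compared by arm. An event that was collected and marked unrelated can still be left out of the drug-related outcome.

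**Working it through.** No sample size, power or event figure in the documents bears on this point, so the check is a comparison of sections.

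**1. What each section requires for each kind of event**

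| Event | DSMB section | Secondary Outcome Measures and Reporting Adverse Events |
|---|---|---|
| AE, probably related | Reviewed and in six-monthly report | Collected |
| AE, possibly related | Reviewed and in six-monthly report | Not stated |
| AE, unrelated | Reviewed and in six-monthly report | Not collected |
| SAE, unrelated | As above, and emailed to the DSMB with source documents | SAE reporting sentence has no exception, but an SAE is an AE, and unrelated AEs are not collected |

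The last two rows conflict. The second is undefined.

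**2. Can the conflict be read away within Reporting Adverse Events?** Partly. The section opens by saying that events are recorded according to criteria given below it, so the instruction to record all AEs could mean all reportable AEs. That would settle the clash between its own sentences, although it sits badly with a definition of AE that disregards relatedness.

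**3. Does that reading also settle the clash with the DSMB section?** No. The DSMB section has no such qualifier, and its three duties (review, periodic report, SAE notification) all use unrestricted wording. The definitions make every SAE an AE, so the exclusion reaches SAEs unless an exception is written, and none is.

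**4. Is the filter well enough specified to be applied uniformly?** No. The unrelated level is defined by timing alone. An event with a timely relationship and a plausible alternative cause is possibly related, but the text does not say whether that counts as related for collection. Nor does it say who makes the judgement. Study drug starts on the day of catheter removal, after an office voiding trial scheduled 1 to 7 days after discharge, so possible drug effects and surgical recovery can overlap. The two sites could log different events.

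**5. The SAE clock.** The DSMB section gives 2 days; Reporting Adverse Events gives two business days and refers back to the DSMB material as its source. For an event learned of on a Friday, 2 days ends on Sunday. Two business days (Monday, Tuesday) ends on Tuesday, which is 4 calendar days.

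**The case against.** The strongest reply is that the related-only scope is deliberate. Secondary Objectives, Secondary Outcome Measures and Reporting Adverse Events all point to drug-related events, and a definition of unrelated is needed to apply such a limit. This stands: the endpoint is a legitimate choice, and having an unrelated category is not in itself a contradiction. But a narrow outcome does not require a narrow collection rule, and the reply leaves the DSMB section unreconciled.

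Three stronger readings are tempting and are not supported.

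- *The filter discards the randomised comparison.* It does not. Related events are still compared by arm, and under Randomization both participants and investigators are masked when causality is judged. Unblinding after an allergic reaction is an exception. The main risk is lost information, not demonstrated bias between arms.
- *The DSMB was blind to serious events.* The text conflicts; it does not show that any SAE was withheld. The DSMB section says that all are sent.
- *The filter costs power on safety.* The documents give no AE rates and plan no safety power, so the answer depends on what is assumed. Take 82 per arm (164/2), a two-sided 0.05 chi-square test with power by exact enumeration, and assumed risks of 20% v 8%: power is 0.61. Dropping half the events in each arm (10% v 4%) gives 0.31. Dropping 4 points of background events from each arm (16% v 4%) gives 0.76. The direction reverses, so no power claim belongs in this point.

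It is also fair to say that new collection rules come late: Statistical Considerations reports that recruitment ceased at 164 and describes the analyses in the past tense. That shapes the fix but does not remove the need for one.

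**Conclusion.** The point holds as an internal inconsistency with a safety consequence. The DSMB section and the AE definition cover all events regardless of cause, while Secondary Outcome Measures and Reporting Adverse Events exclude unrelated ones from collection; no reading of the current wording satisfies both for an SAE judged unrelated. The SAE clock is a second, smaller inconsistency, worth up to two extra calendar days over an ordinary weekend.

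The number of events affected is unknown and cannot be derived from the documents. The conclusion rests only on the wording and on the protocol's own definition of an SAE as a kind of AE. It assumes nothing about event rates, about bias between arms, or about what the sites actually did. The sponsor should correct it; the related-only secondary outcome need not change.

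**What to change.** 1. Replace the two sentences that exclude unrelated events, in Secondary Outcome Measures and in Reporting Adverse Events. Require every SAE to be collected and sent to the DSMB regardless of relatedness, and AEs to be logged with relatedness as a recorded field that includes the possibly related level.
2. Keep the secondary outcome restricted to drug-related events if that is intended, but express it as an analysis restriction. State who judges relatedness and whether possibly related events count.
3. State one SAE reporting clock, in the same words, in the DSMB section and in Reporting Adverse Events.
4. Because recruitment has ended, state which collection rule the sites followed, and confirm from the AE log and DSMB correspondence that all SAEs reached the board. If the filter was applied, describe the AE results as investigator-attributed events only and list this as a limitation.

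The cost is a few sentences and a records check for a trial of 164 women. Where collection is still possible, the downside is logging some routine postoperative events. Events that were never recorded may not be recoverable, which is why item 4 is needed.

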## Adverse Event Definitions

Adverse Event: any untoward medical occurrence, unintended disease or injury, or any untoward clinical signs (including abnormal laboratory finding) in subjects, whether or not related to study medications

Serious Adverse Event: an adverse event that led to:

- Death
- Serious deterioration in the health of the subject that either resulted in
  - A life-threatening illness or injury

- A permanent impairment of a body structure or a body function
- Medical or surgical intervention to prevent life-threatening illness or injury or permanent impairment to a body structure or body function

Unrelated: No evidence that the timing of the AE has a relationship to the time study medications were taken

Possibly Related: The AE has a timely relationship to the study medications, however a potential alternative etiology may be responsible for the AE

Probably Related: The AE has a timely relationship to the study medications and the causative relationship can clearly be established. No potential alternative etiology is apparent.

